4 AIMS AND HYPOTHESES

1. Determine the efficacy of peripheral, central, and combined treatments in alleviating pain among women with VBD-p and VBD-c. We hypothesize that women with VBD-p will preferentially respond to peripheral treatment, while those with VBD-c will preferentially respond to central or combined treatment. To test this hypothesis, we will measure pain in response to standardized tampon insertion with a numeric rating scale and self-reported pain on the McGill questionnaire at the first baseline clinic visit (0) and at 8, 16, and 24 weeks.

2. Determine the efficacy of peripheral, central, and combined treatments in improving patient reported outcomes among women with VBD-p and VBD-c. We hypothesize that women with VBD-c will exhibit more abnormalities in perceived physical, mental, and sexual health compared to those with VBD-p. We also hypothesize that women with VBD-c will demonstrate greater improvement in perceived health with central or combined therapy; while women with VBD-p will demonstrate greater improvement with peripheral treatment. To test these hypotheses, we will measure self-reported physical /mental health with the SF12 and sexual health with the PROMIS questionnaire administered at 0, 8, 16, and 24 weeks.

3. Determine the efficacy of peripheral, central, and combined treatments in normalizing cytokine and microRNA expression profiles in vaginal and blood tissues collected from women with VBD-p and VBD-c. We hypothesize that higher levels of inflammatory mediators in peripheral vaginal samples will be associated with VBD-p, while higher levels in circulating blood will be observed in women with VBD-c. We also hypothesize that peripheral treatment will resolve abnormalities in vaginal biomarkers, while central treatment will resolve abnormalities in blood biomarkers. Finally, we hypothesize that abnormalities in vaginal cytokine and miRNA biomarkers will predict a positive response to peripheral treatment, while abnormalities in blood biomarkers will predict a positive response to central or combined treatment. To test these hypotheses, we will use multiplex assays to measure cytokines and small RNA sequencing to measure miRNAs in samples collected at 0, 8, 16, and 24 weeks.

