To answer questions 1a and 1b, we will fit mixed model repeated measures (MMRM) models which account for missing data as an integral part of the analyses under the assumption of ignorable missing. To answer question 1a, the MMRM model includes longitudinal pain score (0-10 NRS on Tampon Test) as a continuous outcome variable; includes fixed effect terms for treatment (nortriptyline, lidocaine/estradiol, and their interaction), visit, treatment visit interaction, center, and fixed effect covariates vector including age, VBD subtype (binary variable where VBD-c is coded as 0 and VBD-p coded as 1), race (three levels "white", "black" and "other" race, coded into two binary dummy variables with European American serving as a reference level).

Overall treatment effect of nortriptyline, lidocaine/estradiol, and their interaction will be evaluated using an F-test. If significant ($p < 0.05$), treatment differences (each of 3 treatment groups minus placebo) in the Least-Squares means (LS means), their 2-sided 95% CIs, and associated p-

values will be estimated from the MMRM model. P-values will be compared with the significance threshold Bonferroni-corrected for 3 tests (i.e. alpha 0.0166).

To answer question 1b, we will fit a MMRM model analogous to 1a, with additional terms of VBD subtype visit interaction, treatment VBD subtype interaction, and treatment visit VBD subtype interaction. The significance of the additional interaction terms will be evaluated using a F-test comparing the full model in 1b and the reduced model in 1a. Significant ($p < 0.05$) F-test will suggest that the effect of either nortriptyline or lidocaine/estradiol cream, or both, differ by VBD subtype. In this case, we will compare the LS means of the treatment differences in each treatment-VBD-subtype subgroup, after appropriate Bonferroni correction.

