To answer question 3b, we will fit a MMRM model analogous to 1a, with additional terms of treatment cytokine (in blood and vaginal samples) interaction, visit cytokine interaction, and treatment visit cytokine interaction. Significance of additional interaction terms will be evaluated using an F-test. Significant ($p < 0.05$) F-test will suggest that treatment effects by nortriptyline or lidocaine/estradiol cream or both, are modified by cytokines.

Secondary analyses for Aim 3 will include the association of Tier 2 biomarkers (cytokines and miRNAs) with VBD subtype and interaction with treatment response. These analyses will be analogous to those specified for questions 3a and 3b, with p-value thresholds kept at 0.05 due to exploratory nature of these analyses. In our secondary analyses we will also evaluate the change of biomarker concentrations (blood and vaginal samples) over time (at 0, 8, 16, and 24 weeks) in each treatment group and VBD subtype. We hypothesize that these biomarkers may serve as intermediate phenotypes for treatment success in VBD patient subgroups.

Expected Outcomes. 1) Women with VBD-p will have higher levels of inflammatory mediators in peripheral vaginal samples, while women with VBD-c will have higher levels of inflammatory mediators in circulating blood measured at the baseline visit (0 weeks). 2) Abnormalities in baseline vaginal cytokine and miRNA biomarkers will predict a positive response to peripheral lidocaine/estradiol treatment, while abnormalities in blood biomarkers will predict a positive response to centrally-targeted nortriptyline or combined treatment. 3) Peripheral treatment will resolve abnormalities in vaginal biomarkers evaluated at 8, 16, and 24 weeks, while central treatment will resolve abnormalities in blood biomarkers evaluated at 16 weeks.

All analyses will be performed using the Intent-to-Treat (ITT) population. The ITT population will include all randomized participants. Participants will be grouped according to their randomized allocation, regardless of whether the allocated therapy was administered or switched.

Any deviations from the statistical analyses described above, due to unforeseen circumstances, will be documented in the Statistical Analysis Plan (SAP).

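### The question 3b model has no treatment-by-subtype terms, so its F-test cannot tell a cytokine that modifies the treatment effect from one that only marks VBD subtype

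*Combined protocol and SAP*

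**What the plan says.** Model 1a (Section 15.2) has the factorial treatment terms, visit, treatment by visit, center, and a "fixed effect covariates vector including age, VBD subtype (binary variable where VBD-c is coded as 0 and VBD-p coded as 1". Subtype is therefore a main effect only. Model 1b is model 1a "with additional terms of VBD subtype visit interaction, treatment VBD subtype interaction, and treatment visit VBD subtype interaction".

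Model 3b (Section 15.4) starts again from 1a, not 1b: "we will fit a MMRM model analogous to 1a, with additional terms of treatment cytokine (in blood and vaginal samples) interaction". The added terms in full are "additional terms of treatment cytokine (in blood and vaginal samples) interaction, visit cytokine interaction, and treatment visit cytokine interaction". These terms are evaluated by an F-test at 0.05, and the planned reading is: "F-test will suggest that treatment effects by nortriptyline or lidocaine/estradiol cream or both, are modified by cytokines". The secondary analyses of Tier-2 mediators and microRNAs follow the same pattern. No section adds the 1b subtype terms to 3b, and none plans a sensitivity analysis that does.

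Two of the plan's own expectations bear on this. Section 4 hypothesises that "women with VBD-p will preferentially respond to peripheral treatment, while those with VBD-c will preferentially respond to central or combined treatment". The first expected outcome of Aim 3 is that "Women with VBD-p will have higher levels of inflammatory mediators in peripheral vaginal samples", with the reverse pattern in blood.

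**The concern.** A main effect for subtype adjusts the average pain level. It does not adjust the treatment effect. If the treatment effect differs by subtype and the cytokine differs by subtype, the omitted treatment-by-subtype effect loads partly onto treatment by cytokine. This is bias, so more patients do not remove it; they make it easier to detect. It also arises whichever cytokine terms enter the F-test.

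What is at stake is the interpretation of one of Aim 3's two primary statistical questions. Subtype already comes from a check-box COPC survey (Section 15.1). A cytokine that only restates that survey is neither a mechanism nor information beyond subtype, yet the planned wording would credit it with modifying the treatment effect. The ambiguity is greatest when the hypotheses about subtype and cytokines are both correct.

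**Working it through.** **1. The plan's own figure.** Section 15.6 gives no power for 3b. Its only power figure linking cytokines and subtype is for question 3a: 128 VBD-p, 192 VBD-c, 0.4 SD, alpha 0.05/4 = 0.0125, power 0.84. Check: 0.4 × √(128 × 192/320) = 3.505; the two-sided critical value is 2.498; Φ(3.505 − 2.498) = 0.843 (0.839 with the noncentral t). It reproduces.

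**2. Where the bias comes from.** Let p be the VBD-p fraction, d the subtype difference in the cytokine in within-subtype SDs, and e the amount by which a drug's effect differs between subtypes. Within any arm, the slope of subtype on cytokine is γ = d·p(1−p)/(1 + d²·p(1−p)). With a common subtype main effect, the spurious treatment-by-cytokine slope is e·γ in size, whatever that main effect is. With p = 0.4, p(1−p) = 0.24:
- d = 0.4: γ = 0.096/1.0384 = 0.092. At e = 1.35 the slope is 0.125 points per SD; at e = 2 it is 0.185.
- d = 0.8: γ = 0.192/1.1536 = 0.166. At e = 1.35 the slope is 0.225; at e = 2 it is 0.333.

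**3. Inputs for the rejection rates.**
- From Section 15.6: 400 × 0.8 = 320 women, or 80 per arm; SD 2.0; within-subject correlation 0.5; 40% VBD-p; interaction effects of 1.20 and 1.35 points that the plan calls detectable; 2 points as clinically meaningful.
- The 0.4 SD is the plan's minimal detectable difference, not an expected value.
- The 0.8 SD is an assumption. The plan equates 0.4 SD of IL-8 with about 2 pg/mL, so 1 SD is about 5 pg/mL, and the earlier 4 pg/mL difference is 4/5 = 0.8 SD. That compares controls with VBD patients, not the two subtypes.
- Also assumed: three post-baseline visits, complete data, an effect constant over visits, one cytokine value per woman and one cytokine per model, and a cytokine main effect, which the plan does not list.

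**4. Simulated rejection at nominal 5%** for a cytokine that marks subtype and has no effect of its own (1,500 replicates per cell). The joint test has 11 df: 2 for visit by cytokine, plus 3 × 3 for treatment by cytokine across visits. The treatment-by-cytokine test has 3 df.

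| Subtype effect | d (SD) | Joint test | Treatment by cytokine |
|---|---|---|---|
| None | 0.4 | 5.0–5.5% | 5.1–5.2% |
| One drug, 1.20 | 0.4 | 6.1% | 6.9% |
| One drug, 1.35 | 0.4 | 5.4% | 8.6% |
| Both drugs, opposite, 1.35 | 0.4 | 6.5% | 11.9% |
| Both drugs, opposite, 2.0 | 0.4 | 11.3% | 21.9% |
| One drug, 1.35 | 0.8 | 10.3% | 16.9% |
| Both drugs, opposite, 1.35 | 0.8 | 17.6% | 31.5% |
| Both drugs, opposite, 2.0 | 0.8 | 36.1% | 61.5% |

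The Monte Carlo standard error near 5% is √(0.05 × 0.95/1500) = 0.6 percentage points, so 5.4% cannot be told from nominal.

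A simpler single-visit version of the 3-df test, with 80 to 87 women per arm (87 is an assumption) and opposite effects for the two drugs, gives about 9–10% and 13–15% at 0.4 SD for 1.35 and 2 points, and about 20–22% and 40–42% at 0.8 SD.

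**5. With the 1b subtype terms** in both the full and the reduced model, rejection is 4–6% in every scenario.

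**The case against.** The strongest reply is that 3b asks whether biomarkers predict response. A cytokine that tracks a subtype with a different response does predict response, so the planned model gives a legitimate marginal answer. That stands. The fault is in attribution: the planned conclusion is effect modification by the cytokine, and the planned model cannot support it.

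A second reply is that conditioning on treatment by subtype may discard real signal. Section 15.1 says the subtype criteria need more work, and Section 15.4 treats biomarkers as possible intermediate phenotypes. If inflammation is part of how subtype affects response, the adjusted test removes some of what is sought. This also stands, and is why the adjusted test should sit beside the planned one and not replace it.

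A third reply concerns size. A reader might infer that a cytokine marking subtype will be declared a predictor, or that false biomarker claims become likely. The documents do not support that. The F-test in Section 15.4 reads most naturally as one joint test of all added terms, and at 0.4 SD with 1.20 to 1.35 points it rejects only about 5 to 6.5% of the time. The higher rates need 2-point effects or 0.8 SD between subtypes. The documents give no source for 0.8 SD, and Section 3.4 reports blood IL-8 raised in both subtypes. A drug that works in one subtype only is also more extreme than Section 3.2, where topical treatment alleviated pain in 65% of VBD-p and 36% of VBD-c.

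For the Tier-2 mediators the extra error is small beside what the plan already accepts: 32 × 0.05 = 1.6 nominal false positives under the null, in analyses labelled exploratory.

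**Conclusion.** The point holds as a limit on interpretation. Model 3b cannot separate a cytokine that modifies the treatment effect from one that marks subtype, and the plan's own hypotheses supply both conditions for confusing them. At 0.4 SD and 1.35 points the inflation is small: about 5 to 6.5% for the joint test and about 8 to 12% for the treatment-by-cytokine test. At an assumed 0.8 SD, with the two drugs having opposite subtype effects of 1.35 to 2 points, it is about 18 to 36% and 20 to 62%; the low end of the last range comes from the single-visit version.

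These rates rest on the assumptions listed in the check, above all the subtype separation, which the documents do not give. The structural gap does not depend on them. This is a cheap improvement: it changes what a significant 3b result can be said to show, and it does not invalidate 3b as a test of prediction.

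**What to change.** In Section 15.4, specify two versions of 3b:
- **As planned**, on model 1a, reported as the marginal answer to whether the biomarker predicts response.
- **Adjusted**, with the model 1b terms (subtype by visit, treatment by subtype, treatment by visit by subtype) in both the full and the reduced model, so that the cytokine terms are tested over and above subtype.

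State that treatment effects are modified by cytokines beyond subtype only if the adjusted test supports it. Do the same for the exploratory Tier-2 and microRNA analyses.

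The cost is SAP wording, a few degrees of freedom and some power in the adjusted test. In the single-visit model with 87 per arm and a true cream-by-cytokine slope of 0.75 points per SD, power fell from 0.83 to 0.82 at 0.4 SD and from 0.90 to 0.84 at 0.8 SD. The adjusted version may also understate a cytokine through which subtype acts, which is the reason to report both. Specifying both now avoids choosing the model after the results are known.

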15.4 Analysis of the Aim 3 Endpoints

Cytokine Expression levels will be measured in vaginal lavage samples and plasma isolated from whole blood. We will use a standard Human MesoScale Discovery multiplex kit to measure 36 inflammatory mediators (4 tier-1 and 32 tier-2).

Tier-1 mediators include the pro-inflammatory cytokines IL-1 β ,⁵⁹⁻⁶¹ IL-8,^{7,60,62} and IL-17⁶³ and anti-inflammatory cytokine IL-1ra.^{7,61} These cytokines were selected based on previous associations with VBD case status and symptom severity.

Tier-2 mediators include cytokines (e.g., interleukin 6; IL-6), chemokines (e.g., monocyte chemoattractant protein 1; MCP1), and growth factors (e.g., vascular endothelial growth factor; VEGF) that are involved in peripheral and central sensitization, inflammation, and chronic pain.¹²⁸

miRNA Expression levels will be measured in vaginal swab samples and blood. We will isolate total RNA and then ship the RNA to UT Health Genome Sequencing Facility (GSF), directed by [name]. The GSF core will perform small RNA library preparation and sequencing.

Data Analysis. The two primary statistical questions for Aim 3 are: 3a) At baseline, is there an inverse association between VBD 'centralness' score (determined by the number of COPC sites) and the levels of Tier-1 cytokines in vaginal samples; and a positive association between VBD 'centralness' score and the levels of Tier-1 cytokines in plasma samples? 3b) Do biomarkers in vaginal fluid predict response to peripheral treatment and biomarkers in blood predict response to central treatment?

To answer question 3a, we will fit a linear regression model where cytokine level (skewed variables will be transformed (e.g., log, box-cox) to approximate normal distribution) will be a continuous dependent variable and VBD 'centralness' score, will be the main predictor of interest. Covariates will include age and race. Significance of regression coefficient associated with the 'centralness' score will be evaluated using an F-test and significance threshold (alpha) Bonferroni-corrected for the number of cytokines assessed (4 cytokines corresponding to 4 statistical tests). Subgroup means, mean differences and 95% confidence intervals will be output.

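### The F-test written for question 3b, read as a joint test, cannot tell the hypothesised fluid-to-drug pairing from its opposite, and no follow-up contrast is written

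*Combined protocol and SAP*

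**What the plan says.** Section 15.4 lists 3b as one of the two primary statistical questions of Aim 3: "Do biomarkers in vaginal fluid predict response to peripheral treatment and biomarkers in blood predict response to central treatment". The expected outcomes in the same section give the pairing a direction. For the vaginal side: "Abnormalities in baseline vaginal cytokine and miRNA biomarkers will predict a positive response to peripheral lidocaine/estradiol treatment". For the blood side they expect the same for nortriptyline or combined treatment.

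The analysis takes the repeated-measures model of question 1a and enlarges it by "additional terms of treatment cytokine (in blood and vaginal samples) interaction, visit cytokine interaction, and treatment visit cytokine interaction". Then: "Significance of additional interaction terms will be evaluated using an F-test". At p < 0.05, the stated conclusion is that "treatment effects by nortriptyline or lidocaine/estradiol cream or both, are modified by cytokines". Nothing further is written for 3b.

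Question 1b (Section 15.2) goes on to a second step after a significant F-test: "we will compare the LS means of the treatment differences in each treatment-VBD-subtype subgroup, after appropriate Bonferroni correction". Section 15.3 repeats that step for 2b.

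**The concern.** The question pairs a fluid with a drug, and the rule does not. The null of a joint test is that no added term matters: either fluid, any active arm, any visit. A vaginal cytokine that modifies only the nortriptyline effect, or a blood cytokine that modifies only the cream effect, runs against the hypothesis. Either would produce a significant result and the same written conclusion as the hypothesised pattern.

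Visit-by-cytokine is also among the added terms. A cytokine that only tracks pain over time, equally in all arms, could therefore lead to the conclusion that treatment effects are modified.

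At stake is what the trial may claim about biomarkers that predict response. With no named contrast, any statement about which fluid predicts response to which drug would be chosen after seeing the coefficients, without error control.

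**Working it through.** **The plan's own figure.** Section 15.6 gives no power for 3b. Its only Aim 3 figure is for question IIIa (0.4 SD, 192 versus 128, alpha 0.05/4), and it reproduces: 0.4/√(1/192 + 1/128) = 3.505, and Φ(3.505 − 2.498) = 0.84, as stated.

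**Inputs from the documents.** 1:1:1:1 allocation (5.3); 400 women with 20% attrition, so 320, or 80 per arm; SD 2.0; within-subject correlation 0.5 (15.6); visits at 0, 8, 16 and 24 weeks (Section 4).

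**Assumptions.** One cytokine, standardised, measured in both fluids with correlation 0.2; compound symmetry; modification of 0.6 points per SD at weeks 8 and 16 only; about 300 denominator df.

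**Joint test, treatment terms only.** Numerator df = 3 arm contrasts × 4 visits × 2 fluids = 24, or 12 with one fluid per model. The visit covariance is Σ = 4(0.5I + 0.5J), so Σ⁻¹ = 0.5(I − 0.2J). For the profile v = (0, 1, 1, 0), v′Σ⁻¹v = 0.5(2 − 0.2 × 4) = 0.6. If a cytokine modifies one drug,

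λ = slope² × n₁n₂/(n₁ + n₂) × v′Σ⁻¹v = 0.36 × (160 × 160/320) × 0.6 = 17.28.

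The drug enters only through the numbers on and off it, the sign of the slope is squared away, and the fluid does not enter. So λ is 17.28 for vaginal by cream, vaginal by nortriptyline and blood by cream alike. Power is 0.62 at 24 df and 0.78 at 12 df (0.64 and 0.79 with 1,200 denominator df).

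Unequal retention changes little. With 70 in each nortriptyline arm and 90 in each other arm, the nortriptyline split is 140/180 and λ = 0.36 × 78.75 × 0.6 = 17.01.

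Simulation agrees. With both pairings active at 0.5 points per SD and post-baseline visits as outcomes, the joint test rejects in 0.909 (hypothesised) versus 0.901 (opposite) of trials; in a vaginal-only model, 0.659 versus 0.665. Under the null it rejects in 0.050.

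**Visit-by-cytokine terms included.** Now df = 2 fluids × (4 × 4 − 1) = 30. Take a cytokine with slope b at weeks 8, 16 and 24, equal in all arms, and fluid correlation 0. The information per woman and fluid, after removing the cytokine main effect, is 0.6 − 0.3²/0.4 = 0.375, so λ = 2 × 320 × 0.375 × b² = 240b². For b = 0.2, 0.3 and 0.5, λ = 9.6, 21.6 and 60, and the test rejects in 0.31, 0.73 and 0.999 of trials (chi-square reference) although no treatment effect is modified.

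**Week-16 contrast.** For vaginal cytokine by cream, averaged over pill, SE = 2.0 × √(1/160 + 1/160)/√(1 − 0.2²) = 0.228, and 0.6/0.228 = 2.63. Power is Φ(2.63 − 1.96) = 0.75 at 0.05 and Φ(2.63 − 2.73) = 0.46 at 0.05/8.

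**Range over the assumed slope** (λ = 48 × slope²):

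| Slope | λ | Joint, 24 df | Joint, 12 df | Contrast at 0.05/8 |
|---|---|---|---|---|
| 0.4 | 7.68 | 0.26 | 0.37 | 0.16 |
| 0.5 | 12.00 | 0.42 | 0.58 | 0.29 |
| 0.6 | 17.28 | 0.62 | 0.78 | 0.46 |
| 0.8 | 30.72 | 0.91 | 0.98 | 0.78 |

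If the effect builds up, v = (0, 0.5, 1, 0.5), then v′Σ⁻¹v = 0.5(1.5 − 0.2 × 4) = 0.35 and λ = 0.36 × 80 × 0.35 = 10.08. The joint test then has 0.35 (24 df) or 0.49 (12 df), against an unchanged 0.46 for the contrast.

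**Does the contrast discriminate?** In simulation with 0.8 points per SD and fluid correlation 0, two directed week-16 contrasts, each at two-sided 0.025 and counted only in the hypothesised direction, reject in 89–90% of trials under the hypothesised pairing and about 1% under the opposite one.

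**The case against.** Section 15.4 does not say that the terms are pooled. Section 15.2 describes the 1b test as a full-versus-reduced model comparison, and Section 15.3 says that 2b is evaluated jointly; 3b has neither statement. Model 1a codes nortriptyline, cream and their interaction as separate terms, so term-by-term F-tests would separate the drugs. This stands as an alternative reading, and the equal-power result then falls away. The joint reading is still the more natural one, given how 1b and 2b are handled and given a conclusion that does not separate the drugs. Even term-by-term tests would leave direction and the answer to 3b unstated.

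A reader might infer that 62% rejection under the opposite pairing is a false-positive rate about 12 times the nominal 5%. It is not. A cytokine does modify a treatment effect in that scenario, so the null is false, and the plan's broad conclusion is true.

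A reader might also infer that targeted contrasts are generally more powerful. The 0.75 against 0.35 comparison supports that only for an uncorrected contrast, the build-up profile and the 24-df test. With correction, the contrast is often weaker.

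Question 3b does not ask for exclusivity, so proof that the hypothesised slope exceeds the opposite one is not required. Nor do the documents define a sign for each cytokine: they speak of abnormalities, and Section 3.4 reports IL-1ra as reduced in a cited study and increased in VBD-p.

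Finally, Section 12 lists prediction of response by baseline biomarkers as a secondary endpoint. No efficacy conclusion depends on it, and the fitted model already contains every slope needed.

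**Conclusion.** The concern holds on the joint reading: the written rule for 3b does not answer the question it is attached to. With balanced arms, power is the same for the hypothesised and the opposite pairing, about 0.62–0.64 at 24 df or 0.78–0.79 with one fluid per model. The equality does not depend on the assumed slope; the power level does. It becomes approximate when retention and effect sizes both differ: 0.827 versus 0.801 with effects of 0.3 and 0.5 and the retention above, on the 30-df test.

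The visit-by-cytokine problem applies if all added terms are tested, as the text literally says. The missing follow-up applies on either reading.

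This is worth correcting before analysis, but it is moderate in weight. It concerns what may be claimed about predictive biomarkers, not the treatment comparisons, and it does not mean that the data or the model cannot answer 3b.

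**What to change.** In Section 15.4:

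- State that the cytokine values in the 3b model are baseline values, and restrict the F-test to terms that contain treatment. Keep that test as descriptive or as a gatekeeper.
- Answer 3b with prespecified week-16 contrasts from the same model: vaginal Tier-1 cytokine by cream (active versus placebo cream, averaged over pill) and plasma Tier-1 cytokine by nortriptyline (active versus placebo pill, averaged over cream).
- Test them two-sided, corrected over 4 cytokines × 2 pairings = 8 contrasts.
- Report each slope with its sign and confidence interval, and the two opposite pairings beside it.
- Add a formal test of the hypothesised against the opposite slope only if fluid-specific prediction is to be claimed.

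This needs SAP wording and contrasts, but no new data. The price is power: about 46% per contrast at 0.05/8 in the assumed scenario, against 62% (24 df) or 78% (12 df) for the uncorrected joint test when effects are equal at weeks 8 and 16.

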2) Women with VBD-p and VBD-c exhibit unique microRNA expression profiles. MicroRNAs (miRNAs) are small non-coding RNA molecules that regulate expression of $\geq 1/3$ of all human genes by degrading messenger RNA (mRNA) transcripts or by inhibiting mRNA translation.⁶⁷ miRNAs regulate molecular pathways linked to pain, inflammation and immune response.⁶⁸⁻⁷⁶ Differential expression of circulating miRNAs has been reported in chronic pain conditions.⁷² A recent preclinical study on neuropathic pain reported a positive correlation between pain thresholds and miRNA levels in plasma and cerebrospinal fluid.⁶⁹ A clinical study of regional pain syndrome identified 18 miRNAs differentially expressed in blood.⁷² Thus, miRNA expression profiles may also be informative about the pathophysiology VBD. We conducted a study to measure miRNAs in women with VBD; profiling >750 miRNAs in blood from our VBD cohort using OpenArray cards.⁷ Compared to HC, women with VBD-p exhibited a downregulation of 4 and upregulation of 2 miRNAs (Table 3). Three of these miRNAs (miR-449b, miR-133b, and miR-200b) are dysregulated in endometriosis and bladder pain syndrome.^{77, 78} Women with VBD-c exhibited a downregulation of 3 and upregulation of 4 miRNAs. These miRNAs have been associated with cancer,⁷⁹⁻⁸⁴ infectious disorders,⁸⁵ inflammatory disorders,⁸⁶ and orofacial pain.⁸⁷ Four miRNAs were dysregulated in both subtypes. Dysregulation of miR-520f and miR-520D may explain the increased IL-8 levels in women with both VBD-p and VBD-c, as the miR-520 family regulates IL-8.⁸⁸

Table 3. miRNAs dysregulated in VBD-p and VBD-c

VBD-p		
miRNA	Fold Change	P-value
miR-449b	-330.14	0.017
miR-34b	-239.45	0.003
miR-645	-117.87	0.038
miR-503	-92.20	0.037
miR-200b	94.52	0.048
miR-133b	1731.74	0.014
VBD-c		
miRNA	Fold Change	P-value
miR-1825	-19012.5	0.019
miR-1288	-745.74	0.045
miR-593	-56.76	0.019
let-7f-2#	5.77	0.034
miR-512-3p	23.03	0.046
miR-125a-3p	69.59	0.041
miR-661	981.98	0.038
Both		
miRNA	Fold Change	P-value
miR-485-5p	-90.76 / -84.32	0.003 / 0.010
miR-1294	-41.47 / -60.67	0.012 / 0.014
miR-520f	-33.67 / -15.24	0.003 / 0.035
miR-520D-3p	2486.77 / 204617	0.021 / 0.002

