12 OUTCOME DETERMINATIONS

Aim 1. Determine the efficacy of peripheral, central, and combined treatments in alleviating pain among women with VBD-p and VBD-c.

Primary Endpoints:

- Ia. pain score during tampon test at 16 weeks
- Ib. self-reported pain *via* SF-MPQ at 16 weeks

Secondary Endpoints:

- Ila. experimental pain *via* local and remote PPTs at 16 weeks
- Ilb. COPC pain levels *via* COPC follow-up survey at 16 weeks
- Ilc. Pain scores and PPTs at 8 weeks and 24 weeks

Aim 2. Determine the efficacy of peripheral, central, and combined treatments in improving patient reported outcomes among women with VBD-p and VBD-c.

Primary Endpoints:

- Ia. self-reported physical/mental health *via* SF12v2 at 16 weeks
- Ib. sexual health *via* PROMIS at 16 weeks

Secondary Endpoints:

- Ila. mood *via* SCL-27 at 16 weeks
- Ilb. somatic awareness *via* PILL at 16 weeks
- Ilc. perceived stress *via* PSS at 16 weeks
- Ild. sleep *via* sleep scale at 16 weeks
- Ile. Patient reported outcomes at 8 weeks and 24 weeks

Aim 3. Determine the efficacy of peripheral, central, and combined treatments in normalizing cytokine and microRNA expression profiles in vaginal and blood tissues collected from women with VBD-p and VBD-c.

Primary Endpoints:

- Ia. cytokine levels *via* mesoscale discovery assays at 16 weeks
- Ib. microRNA levels *via* sequencing read at 16 weeks

Secondary Endpoints:

- Ila. cytokine and microRNA levels at 8 weeks and 24 weeks
- Ilb. Aim 3 will also identify cytokine and microRNA biomarkers at baseline that predict treatment response at 8, 16, and 24 weeks

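### The exploratory Tier-2 cytokine and microRNA screen has no error-rate control, yet it serves the declared endpoint of identifying predictive biomarkers

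*Combined protocol and SAP*

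**What the plan says.** Section 15.4 sets the Aim 3 assay to "measure 36 inflammatory mediators (4 tier-1 and 32 tier-2". Both analyte classes are taken from two sites: "Cytokine Expression levels will be measured in vaginal lavage samples and plasma isolated from whole blood", and "miRNA Expression levels will be measured in vaginal swab samples and blood".

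The four Tier-1 cytokines have their own questions, 3a (association with the centralness score at baseline) and 3b (modification of the treatment effect). Question 3a is Bonferroni-corrected for four tests. The remaining analytes go to secondary analyses modelled on 3a and 3b, covering "association of Tier 2 biomarkers (cytokines and miRNAs) with VBD subtype and interaction with treatment response", "with p-value thresholds kept at 0.05 due to exploratory nature of these analyses".

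Section 12 lists as secondary endpoint IIb: "Aim 3 will also identify cytokine and microRNA biomarkers at baseline that predict treatment response at 8, 16, and 24 weeks". Section 4 adds a directional hypothesis: vaginal cytokine and microRNA abnormalities should predict response to peripheral treatment, and blood abnormalities response to central or combined treatment.

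The number of microRNAs to be analysed is not given. The nearest figure, in section 3.4, describes an earlier study: "profiling >750 miRNAs in blood from our VBD cohort using OpenArray cards". No section describes false-discovery control, a hold-out sample or a validation step for this screen.

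**The concern.** A per-test 0.05 threshold over a large family produces a list of significant markers whether or not any marker is real. An exploratory label is a fair reason for a looser error rate, but here no rate is set or reported, so a reader cannot tell how much of the list to expect by chance.

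This matters because the plan asks the screen for more than hypothesis generation. The written 3a and 3b models concern the Tier-1 cytokines, so for Tier-2 cytokines and microRNAs the association and prediction parts of Aim 3, including endpoint IIb, rest on the 0.05 rule. The plan is also uneven: it corrects for four tests in 3a and for three outcomes in question 2a of section 15.3, but not in its largest family. What is at stake is whether a marker reported under IIb as predicting response to the cream or to nortriptyline can be told apart from a chance finding.

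**Working it through.** **Inputs.** From section 15.4: 0.05 per test, 32 Tier-2 cytokines, two sample types, two questions. From section 15.6: 128 VBD-p and 192 VBD-c, a difference of 0.4 SD, correction for four tests, stated power 0.84. Assumed: 100 to 750 microRNAs per sample type, the upper end taken from the size of the earlier panel.

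**1. The plan's own figure.** No false-positive rate is stated for the screen; the nearest figure is the Tier-1 power. The standard error in SD units is √(1/128 + 1/192) = 0.114, so the standardised difference is 0.4/0.114 = 3.51. At two-sided 0.05/4 = 0.0125 the critical value is 2.50, and power is Φ(3.51 − 2.50) = 0.84. This reproduces the plan. At an unadjusted 0.05, power is Φ(3.51 − 1.96) = 0.94.

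**2. Cytokines, 3a-type question, no marker real.** Tests: 32 × 2 = 64. Expected false hits: 0.05 × 64 = 3.2. Chance of at least one under independence: 1 − 0.95^64 = 0.962.

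Correlation leaves the expected count at 3.2 but lowers the chance of any hit. Simulation with one common factor over all 64 test statistics gives:

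| Correlation | Chance of at least one false hit |
|---|---|
| 0 | 96% |
| 0.3 | about 86% |
| 0.5 | about 67% |
| 0.7 | about 44% |

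**3. Cytokines, 3b-type question.** Section 15.4 does not make clear whether one model holds a cytokine's blood and vaginal levels together. If it does, there are 32 further tests; if not, 64. With one F-test per model, the two questions together give 96 to 128 tests and 0.05 × 96 = 4.8 to 0.05 × 128 = 6.4 expected false hits. The chance of at least one under independence is 1 − 0.95^96 = 99.3% to 1 − 0.95^128 = 99.9%.

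**4. MicroRNAs.** Per question, with sample types tested separately: 0.05 × 100 × 2 = 10 to 0.05 × 750 × 2 = 75 expected false hits. If a 3b-type model holds both sample types, halve this for that question.

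**5. If some markers are real.** Let π be the share of real markers, each with an effect of 0.4 SD, so that power is 0.94 at 0.05. The false share of hits is 0.05(1 − π) / [0.05(1 − π) + 0.94π].

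- π = 1%: 0.0495 / (0.0495 + 0.0094) = 84%
- π = 5%: 0.0475 / (0.0475 + 0.0470) = 50%
- π = 10%: 0.0450 / (0.0450 + 0.0940) = 32%

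The 0.94 applies to the subtype comparison. Power for the treatment interaction was not computed; lower power would raise these shares.

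**6. The proposed rule.** Benjamini-Hochberg at q = 0.05 in four families (two questions by two analyte classes) gives, if no marker is real and families and tests are independent, a chance of any false finding of 1 − 0.95^4 = 19%. Splitting further by sample type gives eight families and 1 − 0.95^8 = 34%, or 1 − 0.9^8 = 57% at q = 0.10. For comparison, Bonferroni over the 64 cytokine tests (0.05/64 = 0.00078) would cut power for 0.4 SD from 0.94 to 0.56.

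**The case against.** The choice is open and tiered. Four cytokines were selected on prior evidence and corrected in 3a; the rest are secondary and labelled exploratory in the sentence that sets the threshold. That sentence does not say that p < 0.05 makes a marker identified. The word comes from endpoint IIb, which also covers Tier-1 cytokines. For a declared screen, clearly labelled unadjusted p-values are a position some statisticians would defend. This stands, and it keeps the point modest. It does not remove the mismatch with IIb and section 4, nor the absence of any stated error rate.

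A reader might infer several stronger things that the documents do not support:

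- *That most or all reported markers would be false.* This depends on how many are real; at 10% real in the illustration above, about a third of hits are false.
- *That a false hit is always more likely than not.* At correlation 0.7 the figure for 64 cytokine tests is 44%, and no document gives the correlation.
- *That the earlier microRNA results in Table 3 of section 3.4 show the problem.* They compare each subtype with healthy controls on another platform, and the number of tests behind the table is not given.
- *That a primary endpoint is decided at this threshold.* Endpoint "Ib. microRNA levels *via* sequencing read at 16 weeks" concerns level after treatment; the 0.05 sentence covers association with subtype and prediction of response.
- *That the screen is the only analysis linking microRNAs to subtype or treatment.* Section 15.4 also plans change over time by treatment group and subtype, with no threshold stated.

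**Conclusion.** The concern holds as a mismatch between an uncontrolled screen and a declared objective. If no marker is real, the Tier-2 cytokines alone give 3.2 expected false hits on the subtype question, whatever the correlation, and a 96% chance of at least one under independence, falling to about 44% at correlation 0.7. The 3b-type question adds 32 to 64 cytokine tests. MicroRNAs add 10 to 75 expected false hits per question if 100 to 750 are tested separately in each sample type; that count is an assumption. The false share among reported hits cannot be fixed from the documents. It is about 50% if 5% of markers are real and power is 0.94. Because the plan labels the screen exploratory, this is a cheap improvement and not a threat to the trial's main conclusions.

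**What to change.** In section 15.4, keep the screen exploratory but replace the unadjusted 0.05 rule with Benjamini-Hochberg control at a stated q, for example 0.05, within each combination of question (3a-type, 3b-type) and analyte class (Tier-2 cytokine, microRNA), pooled over the two sample types. Report unadjusted p-values beside the q-values so that no candidate is hidden. For endpoint IIb, use 'identified' or 'predicts' for these analytes only when they pass.

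Two disclosures belong with it: that four families at q = 0.05 leave about a 19% chance of some false finding under a global null with independence, and whether the 3b-type models hold both sample types together.

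The cost is a few sentences in section 15.4 and a standard adjustment step. The downside is a shorter candidate list and less power for weak single markers.
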